4.4.1 Clinical Criteria for Early Study Termination

A primary objective of this early Phase 1 study is to identify the maximum safe and well-tolerated dose and/or dosing regimen that achieve PK, pharmacodynamic, and/or biologic targets in humans based on preclinical or early clinical data. Therefore, it is possible that study participants may not receive all doses specified in the protocol if this objective is achieved at lesser dose levels in this study. This would not be defined as early termination of the study, but rather an earlier than anticipated achievement of the study objective(s). If a finding (eg, PK, pharmacodynamic, efficacy, biologic targets, etc.) from another preclinical or clinical study using the study intervention(s), comparator(s), drug(s) of the same class, or methodology(ies) used in this study results in the study(ies) or program being stopped for nonsafety reasons, this also does not meet the definition of early study termination.

Early study termination is defined as a permanent discontinuation of the study due to unanticipated concerns of safety to the study participants arising from clinical or preclinical studies with the study intervention(s), comparator(s), drug(s) of the same class, or methodology(ies) used in this study.

5 STUDY POPULATION

Male/Female participants with group 1 PAH between the ages of 18 and 70 years (inclusive).

Prospective approval of protocol deviations to recruitment and enrollment criteria, also known as protocol waivers or exemptions, is not permitted.

5.1 Inclusion Criteria

To be eligible for inclusion in this study, the participant must:

1. Be judged to have no untreated, clinically significant health issues from other co-morbidities (e.g. uncontrolled diabetes) based on medical history, physical examination, vital sign (VS) measurements and electrocardiograms (ECGs) performed at screening visit.

2. Be judged to have no untreated, clinically significant health issues from other co-morbidities (e.g. uncontrolled diabetes) based on laboratory safety tests obtained at the screening visit(s). Appendix 2 provides a table of laboratory safety tests to be performed. Appendix 9 provides an algorithm for the assessment of out of range laboratory values.
3. Have a Body Mass Index (BMI) ≤ 35 kg/m², inclusive at screening. See Section 8.3 for criteria on rounding to the nearest whole number. BMI = weight (kg)/height (m)². Weight should not exceed 160 kg.

Demographics

4. Participant is male or female.

(Panel A)

5. Participant is from 18 years to 70 years of age inclusive, at the time of signing the informed consent.

(Panel B, C and D)

6. Participant is from 18-70 years of age inclusive, at the time of signing the informed consent.

Female Participants

- A female participant is eligible to participate if she is not pregnant or breastfeeding, and at least one of the following conditions applies:
 - She is a woman of nonchildbearing potential (WONCBP), as defined in Appendix [5]
- OR
- Is a WOCBP and using a contraceptive method that is highly effective (with a failure rate of <1% per year), with low user dependency or be abstinent from heterosexual intercourse as their preferred and usual lifestyle (abstinent on a long term and persistent basis), as described in Appendix [5] during the intervention period and for at least 14 days corresponding to the time needed to eliminate any study intervention(s) after the last dose of study intervention and agrees not to donate eggs (ova, oocytes) to others or freeze/store for her own use for the purpose of reproduction during this period. The investigator should evaluate the potential for contraceptive method failure (ie, noncompliance, recently initiated) in relationship to the first dose of study intervention.

- A WOCBP must have a negative highly sensitive pregnancy test (urine or serum as required by local regulations) within 24 hours before the first dose of study intervention.
- If a urine test cannot be confirmed as negative (eg, an ambiguous result), a serum pregnancy test is required. In such cases, the participant must be excluded from participation if the serum pregnancy result is positive.
- Additional requirements for pregnancy testing during and after study intervention are located in Appendix [2].
 - The investigator is responsible for review of medical history, menstrual history, and recent sexual activity to decrease the risk for inclusion of a woman with an early undetected pregnancy.

Male Participants

Male participants are eligible to participate if they agree to the following during the intervention period and for at least 14 days, corresponding to time needed to eliminate study intervention(s) after the last dose of study intervention)]

- Be abstinent from heterosexual intercourse as their preferred and usual lifestyle (abstinent on a long term and persistent basis) and agree to remain abstinent
- OR
- Must agree to use contraception unless confirmed to be azoospermic (Vasectomized or secondary to medical cause [Appendix 5]) as detailed below:

Agree to use a male condom plus partner use of an additional contraceptive method when having penile-vaginal intercourse with a WOCBP who is not currently pregnant. Note: Men with a pregnant or breastfeeding partner must agree to remain abstinent from penile-vaginal intercourse or use a male condom during each episode of penile-vaginal penetration

Informed Consent

7. The participant provides written informed consent for the study. The participant may also provide consent for future biomedical research. However, the participant may participate in the main study without participating in future biomedical research.

Additional Categories

8. Is willing to comply with the study restrictions (see Section 5.3 for a complete summary of study restrictions).

9. Be or have suspected Group 1 pulmonary hypertension as defined by the Nice 2013 Clinical Classification, including:

Pulmonary arterial hypertension (PAH)

- 1.1. Idiopathic PAH
 - 1.2. Heritable
 - a) BMPR2
 - b) ALK1, endoglin, SMAD9, CAV1, KCNK3
 - c) 1.2.3. Unknown
 - 1.3. Drug and toxin-induced
 - 1.4. Associated with
 - d) 1.4.1. Connective tissue disease
 - e) 1.4.4. Congenital heart disease (unrepaired and not requiring repair or repaired simple cardiac defects at least 1-year status post corrective surgery, with no clinically significant residual shunt)
10. Be deemed clinically stable by the investigator.
11. Have a hemoglobin (Hgb) of > 75% of the lower limit of the normal range (at screening visit).
12. Have a clinical indication for RHC as part of initial work-up or ongoing medical management.
- a. **(Panel A) Inclusion Criteria** Have history of right heart catheterization within three years of starting study medication demonstrating mean pulmonary artery pressure of ≥ 27 mmHg and PVR of ≥ 300 dynes/sec/cm⁵ (RHC may have been performed prior to initiation of participant's prescribed background therapy); if subject is status post-surgical repair of congenital heart defect, these criteria must be met at least one year after surgery.

(Panel B, C and D) Inclusion Criteria

- b. Have history of right heart catheterization within three years of starting study medication demonstrating mean pulmonary artery pressure of ≥ 27 mmHg and PVR of ≥ 300 dynes/sec/cm⁵ (RHC may have been performed prior to initiation of participant's prescribed background therapy); if subject is status post-surgical repair of congenital heart defect, these criteria must be met at least one year after surgery.

OR

Have an echocardiogram performed by the investigator (or appropriate designee) at screening or within 1 year of screening demonstrating pulmonary artery systolic pressure ≥ 50 mmHg in conjunction with one or more of the following: tricuspid regurgitation velocity > 3.0 m/s and or significant right heart enlargement and or reduced right heart function.

5.2 Exclusion Criteria

The participant must be excluded from the study if the participant:

Medical Conditions

1. Has pulmonary hypertension subtypes including the following according to Nice 2013

Clinical Classification:

- 1.4.2. HIV infection
- 1.4.3. Portal hypertension
- 1.4.5. Schistosomiasis
- 1.4.6. Chronic hemolytic anemia
- 1'. Pulmonary veno-occlusive disease (PVOD) and or pulmonary capillary hemangiomatosis (PCH) 1". Persistent pulmonary hypertension of the newborn (PPHN)
2. Pulmonary hypertension owing to left heart diseases
 - 2.1. Left ventricular Systolic dysfunction
 - 2.2. Left ventricular Diastolic dysfunction
 - 2.3. Valvular disease
 - 2.4 Congenital/acquired left heart inflow/outflow tract obstruction and congenital cardiomyopathies
3. Pulmonary hypertension owing to lung diseases and/or hypoxia
 - 3.1. Chronic obstructive pulmonary disease
 - 3.2. Interstitial lung disease
 - 3.3. Other pulmonary diseases with mixed restrictive and obstructive pattern

- 3.4. Sleep-disordered breathing
- 3.5. Alveolar hypoventilation disorders
- 3.6. Chronic exposure to high altitude
- 3.7. Developmental abnormalities
4. Pulmonary hypertension defined as Chronic thromboembolic pulmonary hypertension [CTEPH])
5. Pulmonary Hypertension with unclear multifactorial mechanisms
 - 5.1. Hematologic disorders: chronic hemolytic anemia, myeloproliferative disorders, splenectomy
 - 5.2. Systemic disorders: sarcoidosis, pulmonary Langerhans cell histiocytosis, lymphangioleiomyomatosis, neurofibromatosis, vasculitis
 - 5.3. Metabolic disorders: glycogen storage disease, Gaucher disease, thyroid disorders
 - 5.4. Others: tumoral obstruction, fibrosing mediastinitis, chronic renal failure, segmental pulmonary hypertension
2. Has a history of clinically significant endocrine (not including stable diabetes mellitus), gastrointestinal, cardiovascular, hematological, hepatic (not including chronic stable Hep B and C), immunological, renal, respiratory, genitourinary, or major neurological (including stroke and chronic seizures) abnormalities or diseases. Participants with a remote history of uncomplicated medical events (eg, uncomplicated kidney stones, as defined as spontaneous passage and no recurrence in the last 5 years, or childhood asthma) may be enrolled in the study at the discretion of the investigator. Participants with controlled hypertension are allowed to be enrolled.
3. Is mentally or legally incapacitated, has significant emotional problems at the time of prestudy (screening) visit or expected during the conduct of the study or has a history of clinically significant psychiatric disorder that the investigator feels poses a risk to the participant if they participate in the study. Participants who have had situational depression may be enrolled in the study at the discretion of the investigator.
4. Has a history of cancer (malignancy).

Exceptions: (1) Adequately treated nonmelanomatous skin carcinoma or carcinoma in situ of the cervix or; (2) Other malignancies which have been successfully treated with appropriate follow up and therefore unlikely to recur for the duration of the study, in the opinion of the investigator and with agreement of

the Sponsor (eg, malignancies which have been successfully treated ≥ 10 years prior to the prestudy [screening] visit).

5. Has a history of significant multiple and/or severe allergies (eg, food, drug, latex allergy), or has had an anaphylactic reaction or significant intolerability (ie, systemic allergic reaction) to prescription or non-prescription drugs or food. This includes milk or lactose allergy/intolerance.
6. Has known hypersensitivity to iodine or iodine containing products.
7. Is positive for HIV.
8. Had major surgery, donated or lost 1 unit of blood (approximately 500 mL) within 4 weeks prior to the prestudy (screening) visit.
9. Has persistent or permanent atrial fibrillation with an uncontrolled ventricular rate (i.e. ventricular rate ≥ 90 bpm) (participants with paroxysmal or controlled atrial fibrillation with no clinically significant arrhythmia may be allowed per the judgment of the investigator).
10. Has significantly impaired gas exchange.
11. Has an active respiratory infection (e.g. common cold, bronchitis, influenza, pneumonia) with lung function values (FEV₁ and/or FVC) outside of the normal range at pre-dose Period 1 (May be rescreened upon resolution of the active respiratory infection).

Prior/Concomitant Therapy

12. Is currently on monotherapy calcium channel blockers as a specific treatment for pulmonary hypertension based on a history of positive vasoreactivity testing.
13. Has taken nitrates within 24 hours of anticipated dosing.
14. Has taken inhaled prostacyclin within 24 hours of anticipated dosing (iloprost or treprostinil).
15. Has taken diltiazem immediate release taken within 24 hours or extended release taken within 48 hours of anticipated dosing.
16. Has taken sildenafil or vardenafil within 24 hours or tadalafil within 7 days of anticipated dosing. Participants in whom sildenafil, vardenafil or tadalafil has been stopped prior to these respective time points are eligible.
17. Has taken sGC activator for PAH within 24 hours of anticipated dosing.
18. Has taken endothelin receptor antagonists (ERAs) (e.g. bosentan, ambrisentan, macitentan) within 24 hours of anticipated dosing.

19. Is unable to refrain from or anticipates the use of any medication, including prescription and nonprescription drugs or herbal remedies beginning approximately 2 weeks (or 5 half-lives) prior to administration of the initial dose of study drug, throughout the study (including washout intervals between treatment periods), until the poststudy visit. There may be certain medications that are permitted (see Section 6.5).

Prior/Concurrent Clinical Study Experience

20. Has participated in another investigational study within 4 weeks (or 5 half-lives, whichever is greater) prior to the prestudy (screening) visit. The window will be derived from the date of the last visit in the previous study.

Diagnostic Assessments

21. Has a QTc interval ≥ 470 msec (for males) or ≥ 480 msec (for females) at screening and Predose Period 1
22. Has a systolic BP < 100 mmHg, Diastolic BP < 40 mmHg or HR > 100 /min at baseline. Mean of these values will be used at screening and Predose Period 1. (See exclusion criteria #9 for HR associated with uncontrolled a-fib).
23. Participant has an estimated creatinine clearance of < 60 mL/min based on the Cockcroft-Gault equation; the Cockcroft-Gault equation is at screening:

$$Cl_{Cr} = \frac{(140 - \text{age}[\text{yr}])(\text{body wt}[\text{kg}])}{(72)(\text{serum creat}[\text{mg/dL}])}$$

When creatinine is measured in micromole/litre, use the following formula: (for females multiply result by 0.85)

$$Cl_{Cr} = \frac{(140 - \text{age}[\text{yr}])(\text{body wt}[\text{kg}])}{(72)(\text{serum creatinine}[\text{micromol/L}] \times 0.0113)}$$

An actual creatinine clearance, as determined by a 24-hour urine collection, may be used in place of, or in conjunction with, the Cockcroft-Gault equation.

Other Exclusions

24. Is unable to correctly use the TWISTHALER[®] device (after instruction by the study staff) at a visit prior to randomization.
25. Is under the age of legal consent.
26. Does not agree to follow the smoking restrictions as defined by the CRU.
27. Part 2 only: Suffers from claustrophobia and would be unable to undergo CT scan.

28. Part 2 only: Has participated in a PET research study or other study involving administration of a radioactive substance or ionizing radiation within 12 months prior to the screening visit or has undergone or plans to have extensive radiological examination within this period with a radiation burden over 10 mSv (such as a CT scan exam or nuclear medical exam).
29. Consumes greater than 3 glasses of alcoholic beverages (1 glass is approximately equivalent to: beer [354 mL/12 ounces], wine [118 mL/4 ounces], or distilled spirits [29.5 mL/1 ounce]) per day. Participants who consume 4 glasses of alcoholic beverages per day may be enrolled at the discretion of the investigator.
30. Consumes excessive amounts, defined as greater than 6 servings (1 serving is approximately equivalent to 120 mg of caffeine) of coffee, tea, cola, energy drinks, or other caffeinated beverages per day.
31. Is a regular user of cannabis, any illicit drugs or has a history of drug (including alcohol) abuse within approximately 12 months. Participants must have a negative urine drug screen (UDS) prior to randomization or assignment of allocation number.
32. Presents any concern by the investigator regarding safe participation in the study or for any other reason the investigator considers the participant inappropriate for participation in the study.

5.3 Lifestyle Considerations

Women of childbearing potential (WOCBP) can be enrolled.

5.3.1 Meals and Dietary Restrictions

5.3.1.1 Diet Restrictions

Part 1 Periods 1-3, Part 2 Period 1

In each treatment period, participants will fast from all food and drinks, except water, for at least 8 hours prior to study drug administration and lab safety tests. Participants will fast from all food and drinks except water between study drug administration and the first scheduled meal. Standardized meals will be provided by the investigator at about 4 and 10 hours post-dose. A snack will be offered at about 7 and 13 hours post dose. Participants will fast from all food and drinks except water between meals and snacks. The caloric content and composition of meals will be the same in each treatment period. After the 24-hour postdose procedures have been completed, subsequent meals and snacks will be unrestricted in caloric content, composition and timing.

Part 2 Periods 2-3 (RHC and FRI Periods)

Participants will fast from all food and drink except water for at least 4 hours prior to lab safety tests, study drug administration or insertion of the RHC or the start of the baseline CT scan. In the RHC Period, participants may be permitted a snack at approximately 2 hours post dose and a standard meal at the completion of the RHC procedure, after which they may be given a meal at the investigator's discretion. After completion of dosing in the FRI Period, snacks may be provided by the investigator between the 1 and 3 hour post dose scans and a standard meal will be provided about 1 hour after the 3 hour post dose scan. At the investigator's discretion, subsequent meals and snacks will be unrestricted in caloric content, composition and timing.

In both parts, up to 240 mL of water may be provided after the last inhalation of study drug. Water will be restricted 1 hour prior to initial inhalation and 1 hour after the last inhalation of study drug in each period.

Instructions on whether to take MK-5475 with or without food and/or drink may be modified during the study based on newly available data.

5.3.1.2 Fruit Juice Restrictions

Participants will refrain from the consumption of grapefruit juice, grapefruits, and grapefruit products beginning approximately 2 weeks prior to administration of the initial dose of study drug, throughout the study including the washout intervals between treatment periods and until the poststudy visit.

Participants also will refrain from the consumption of all fruit juices 24 hours prior to and after study drug administration. On all other days during the study, consumption of fruits and fruit juices (except for grapefruit, grapefruit juices, and grapefruit products) is allowed.

5.3.2 Caffeine, Alcohol, and Tobacco Restrictions

5.3.2.1 Caffeine Restrictions

Participants will refrain from consumption of caffeinated beverages or xanthine-containing products from 12 hours prior to the prestudy and poststudy visits and from 12 hours prior to and after study drug administration in each treatment period. At all other times, caffeinated beverages or xanthine-containing products will be limited to no more than 6 units per day amounts (>6 units: 1 unit = 120 mg of caffeine).

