3 HYPOTHESES, OBJECTIVES, AND ENDPOINTS

Hypotheses are aligned with objectives in the Objectives and Endpoints table.

This study is to be conducted in male and female participants with group 1 pulmonary arterial hypertension (PAH).

Objectives	Endpoints
Primary	

 To evaluate the safety and tolerability of MK-5475 in participants with pulmonary arterial hypertension (PAH). (All parts) 	Safety and tolerability will be evaluated during clinical assessments that include vital signs, safety laboratory testing, physical examinations, ECG readings, PFTs and review of adverse events.

 To assess the duration and effect following a single inhaled dose of MK-5475 on pulmonary vascular resistance (PVR) in participants with pulmonary arterial hypertension (PAH). (Part 2, Period 2 (Panel A) and Period 3 (Panels B, C and D)) 	Peak reduction from baseline in PVR after a single inhaled dose of MK-5475
Secondary	

 To estimate the effect of MK-5475 given as single inhaled doses on systemic hemodynamic parameters (heart rate (HR), systolic and diastolic blood pressure (BP)) in participants with pulmonary arterial hypertension. (Part 2 Period 2 (Panel A) and Period 3 (Panels B, C and D)) 	
 HR and BP change from baseline at 0.5, 4.5, and 24 (or prior to discharge) hours post-dose.

 To obtain preliminary plasma pharmacokinetic (PK) data of MK-5475 (e.g. area under the curve (AUC) 0-24, AUC 0-∞, C_{max}, C₂₄, T_{max}, t_{1/2}) in participants with pulmonary arterial hypertension. (Part 1 and 2) 	
 AUC 0-∞, AUC 0-24, C_{max}, C₂₄, T_{max}, apparent terminal half-life

 To assess the effect following a single inhaled dose of MK-5475 on pulmonary blood volume (PBV) in participants with pulmonary arterial hypertension. (Part 2, Period 3 (Panel A) and Period 2 (Panels B, C and D)) 	
 Increases from baseline PBV at 1, 3, 8 and 24 hours postdose.

Objectives	Endpoints
Tertiary/Exploratory	

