5.3.2.2 Alcohol Restrictions

Participants will refrain from consumption of alcohol 24 hours prior to the prestudy and poststudy visits and from 24 hours prior to and after study drug administration in each treatment period. At all other times, alcohol consumption is limited to no more than approximately 3 alcoholic beverages or equivalent (1 glass is approximately equivalent to:

beer [354 mL/12 ounces], wine [118 mL/4 ounces], or distilled spirits [29.5 mL/1 ounce]) per day.

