5.3.2.3 Tobacco Restrictions

Participants will not be permitted to smoke 24 hours prior to and on the day of dosing. At all other times, participants will follow the smoking restrictions (and if applicable, the use of nicotine/nicotine-containing products) defined by the Clinical Research Unit (CRU).

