8.1.11 Domiciling

In Part 1 Periods 1-3 and Part 2 Period 1, participants may report to the clinical research unit (CRU) the evening prior to the scheduled day of administration of the study intervention at the discretion of the investigator. Participants will remain in the unit until the 24-hour, postdose procedures have been performed.

In Part 2, participants will report to the clinic at the time instructed by the CRU in preparation for the CT scan and dosing procedures in the FRI period and the RHC and dosing procedures in the RHC Period.

In the FRI Period, participants will be discharged approximately 1 hour following completion of the 8 hour post dose CT scan but, participants may remain domiciled overnight in preparation for the 24 hour CT scan, at the discretion of the investigator. Those participants that are discharged after 8 hour CT scan will be asked to return for the 24 hour CT scan and discharge procedures.

In the RHC Period, participants will remain domiciled overnight or may be discharged on the same day at the discretion of the investigator if the following discharge criteria are met:

- If present, resolution of any hemodynamic-related clinically significant symptoms with potential relationship to study intervention/procedure
- BP and HR are within 25% of baseline measures
- Participants have a SBP \geq 90 mmHg, HR $<$ 110 bpm (Triplicate HR and BP should be measured at least three times separated by a minimum of 15 minutes. The median values of each set of measurements must meet the criteria above in order to be eligible for same day discharge).
- All AEs have been reviewed by the investigator who confirms clinical appropriateness for same day discharge.

At the discretion of the investigator, participants may be requested to remain in the CRU longer.

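### The caffeine and smoking limits end before the 24 h secondary readings; the 24 h pulmonary blood volume scan is the one clearly exposed

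*Combined protocol and SAP*

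**What the plan says.** **Caffeine (5.3.2.1).** Participants abstain "and from 12 hours prior to and after study drug administration in each treatment period". Outside that window, "At all other times, caffeinated beverages or xanthine-containing products will be limited to no more than 6 units per day". One unit is 120 mg. The same section requires 12 caffeine-free hours before the prestudy and poststudy visits.

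**Smoking (5.3.2.3).** "Participants will not be permitted to smoke 24 hours prior to and on the day of dosing". After that, "At all other times, participants will follow the smoking restrictions" set by the clinical research unit; the documents do not give their content.

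**Alcohol and fruit juice (5.3.2.2, 5.3.1.2).** Alcohol is barred "from 24 hours prior to and after study drug administration in each treatment period". Participants also "refrain from the consumption of all fruit juices 24 hours prior to and after study drug administration".

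**Endpoints.** Section 3 lists "HR and BP change from baseline at 0.5, 4.5, and 24 (or prior to discharge) hours post-dose" for the right heart catheterization (RHC) period, and PBV at 1, 3, 8 and 24 h for the functional respiratory imaging (FRI) period. Section 9.6 models both as change from predose, including 24 h. The Section 9.1 summary lists PBV at 1, 3 and 8 h only.

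**Where participants are (8.1.11).** In the FRI period they may leave about an hour after the 8 h scan: "Those participants that are discharged after 8 hour CT scan will be asked to return for the 24 hour CT scan and discharge procedures". During the RHC period they stay overnight or, if discharge criteria are met, leave the same day.

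**Food and drink in Part 2 Periods 2-3 (5.3.1.1).** A water-only fast of at least 4 h precedes safety labs, dosing, catheter insertion and the baseline CT scan. Later meals and snacks may be unrestricted at the investigator's discretion.

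**The concern.** A change from baseline can be read as a drug effect only if the two readings are taken under like conditions. Here the baseline follows at least 12 h without caffeine and 24 h without smoking, and the 24 h reading need not. Part 2 is open label without placebo (6.3.3), so a stimulant effect at 24 h cannot be separated from a late drug effect. The schedule of activities has no item for caffeine or tobacco intake at 24 h, so affected readings could not be identified afterwards.

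The 24 h scan carries some weight. RHC measurements stop at 4.5 h, so it is the only planned pulmonary pharmacodynamic measurement after 8 h, and the only late evidence on how long the effect lasts.

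**Working it through.** The plan states no figure to reproduce: Section 9.9 gives no variability estimate and no power calculation. The check compares time windows.

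**1. Baseline conditions.** Baseline HR/BP is taken within 3 h before dosing (8.3.2.1) and the baseline CT within 30 min before dosing (8.11.5). Both lie inside the 12 h caffeine and 24 h smoking windows.

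**2. Endpoint times against the caffeine window.** The readings at 0.5 and 4.5 h (HR/BP) and at 1, 3 and 8 h (PBV) fall within 12 h of dosing. Only 24 h falls outside. Time not covered: 24 − 12 = 12 h. Daily cap in that time: 6 × 120 mg = 720 mg.

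**3. Smoking.** If dosing is at clock time T hours after midnight, the dosing day ends 24 − T hours after the dose. That leaves T hours before a reading at 24 h, governed only by the unit's own rules.

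**4. What else protects each 24 h reading.**

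| | 24 h PBV scan (FRI) | 24 h HR/BP (RHC) |
|---|---|---|
| Safety labs at that visit | None scheduled | Yes, in the column for 24 h or discharge |
| 4 h water-only fast | Not triggered; the rule names the baseline scan only | Triggered by the labs |
| Location | May be at home after the 8 h scan | In the unit, or measured before leaving |
| Caffeine time not covered | 12 to 24 h post-dose (12 h) | 12 to 20 h post-dose (24 − 4 = 20; 8 h), if kept overnight |

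A participant discharged on the day of catheterization is measured on the dosing day. The smoking ban then still applies, and the caffeine ban does too if discharge comes within 12 h of dosing.

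**5. Size, under assumptions only.** If a share p of participants is exposed and each shifts by d, the mean 24 h change is biased by p × d. For PBV, d is on the log scale. The documents supply neither p nor d, nor an SD.

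To show scale, take a one-sample t interval as a simplification of the mixed models. Its 95% half-width is t(0.975, n − 1)/√n in SD units:

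- n = 8 (Panel A): 2.365/√8 = 0.84 SD
- n = 12 (Panels B and C at the Table 1 maxima, 4 + 8): 2.201/√12 = 0.64 SD

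Coverage from the noncentral t, with noncentrality equal to the shift in SD units × √n:

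| Shift in the mean | n = 8 | n = 12 |
|---|---|---|
| 0.15 SD | 93.4% | 92.4% |
| 0.40 SD | 83.4% | 75.5% |

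The consequence runs from negligible to material, depending on a shift that the documents do not allow anyone to estimate.

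**The case against.** **The HR/BP reading is largely protected.** This stands. A reader might infer that coffee just before the 24 h HR/BP reading is allowed, and so could imitate or hide a late systemic effect. The text does not support that. The 4 h fast before the labs in the same column bars it, the sentence on unrestricted meals and snacks does not expressly cancel that fast, and participants are in the unit or measured before discharge.

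**The smoking gap is unproven.** This stands in part. The unit's rules may forbid smoking before the scan, and exclusion criterion 26 removes anyone who will not follow them. One cannot say that a cigarette before the scan is permitted, only that the protocol itself does not rule it out.

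**Nothing in the documents says that caffeine or nicotine changes PBV.** This is correct, and it is why no size is claimed. A reader might also be tempted to attach a bias in mmHg or a fixed loss of coverage; that would rest wholly on outside figures.

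**A late drug effect is unlikely.** The plasma half-life is about 2 h (4.3.3), so 24 h is 12 half-lives and 0.5^12 = 0.02% remains. This lowers the stakes. It does not remove the point: where the true change is near zero, a stimulant shift would be the main thing seen, and the plan still chose to scan at 24 h.

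**The study tests no hypotheses** (9.8). True, but it reports 24 h estimates, and those can be biased without any test.

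**Conclusion.** The mismatch is real and confined to the 24 h secondary readings. It matters most for the 24 h PBV scan in participants who go home after the 8 h scan: 12 h of uncontrolled caffeine, smoking left to unseen unit rules, no fast and no control group. For HR/BP what remains is caffeine taken about 12 to 20 h after dosing by those kept overnight. Primary PVR, which ends at 4.5 h, and every endpoint reading to 8 h are untouched.

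The plan's own practice supports closing the gap: alcohol and fruit juice are barred to 24 h, and caffeine is barred before the prestudy and poststudy visits. The size of any bias is unknown. The conclusion assumes that PBV at 24 h will be analyzed, as Sections 3, 9.4 and 9.6 say; if the shorter list in Section 9.1 governs, little remains. Low severity: a cheap improvement, not a threat to the study's main results.

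**What to change.** In 5.3.2.1 and 5.3.2.3, run the post-dose caffeine and smoking restrictions to completion of the 24 h post-dose procedures in the FRI and RHC periods. State that this includes FRI participants discharged after the 8 h scan. It brings both rules into line with the 24 h window already used for alcohol and fruit juice, and the uncovered caffeine time falls from 12 h to 0 h.

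Add one question on caffeine and tobacco intake to the 24 h visit, and say in 9.6 that non-compliant 24 h readings will be flagged in the PBV and HR/BP analyses. Bring the PBV times in 9.1 into line with 9.6.

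The cost is two wording changes, one recorded item and a sentence in the analysis plan. Participants bear about 12 more hours without caffeine per dose, and for smokers the hours from the end of the dosing day to the 24 h procedures.
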